3.4.4.2 Subject Screening and Numbering

After the subject has signed an IRB-approved informed consent form, he/she will be assigned a unique screening number. At each site, the screening numbers will start with S001. Subjects who meet the inclusion and exclusion criteria will be eligible for the study. In the comparative phase, randomization will occur intra-operatively, and a randomization number will be assigned to identify the enrolled subject.

3.4.4.3 Subject Withdrawal or Discontinuation

If a subject discontinues early from the study, the reason should be recorded in source documentation and the CRF. If the subject is withdrawn due to an adverse event, the adverse event should be indicated as the reason for withdrawal. All subjects have the right to withdraw at any point during the study without prejudice. The Investigator (in consultation with the sponsor) can discontinue a subject's participation at their discretion at any time if medically necessary or in the case of non-compliance with the study protocol at.

The investigator shall promptly notify the sponsor when a subject is withdrawn or if the trial is stopped at a clinical site. For subjects that withdraw early (Early Termination), all efforts should be made to collect End of Study data points prior to discontinuation.

3.4.4.4 Subject Replacement

Once a subject is randomized, they may not be replaced.

3.5 Study Endpoints

3.5.1 Safety Endpoints

Primary Safety Endpoint

- 1. The rate of occurrence of Serious Adverse Events (SAEs) at 3 months
- 2. The rate of occurrence of Adverse Experiences (AEs) or Unanticipated Adverse Device Effects at 3 months

Secondary Safety Endpoints

1. The rate of occurrence of SAEs, AEs and/or UADEs at 6, 9 and 12 months

3.5.2 Efficacy Endpoints

Primary Efficacy Endpoints

- 1. The change in VAS score at 3 months compared to baseline (pilot phase)
- 2. The change in VAS score at 12 months compared to baseline (comparative phase)

Secondary Efficacy Endpoints

- 1. The change in VAS score at 1, 3, 6, 9 and 12 months compared to baseline
- 2. The change in PROMIS® score at 1, 3, 6, 9 and 12 months compared to baseline
- 3. The change in FHSQ score at 1, 3, 6, 9 and 12 months compared to baseline
- 4. Changes in pain medication use at 1, 3, 6, 9 and 12 months compared to baseline
- 5. Rate of recurrence of symptomatic neuroma within 12 months

3.6 Assessments, Questionnaires, Surveys, Diaries

3.6.1 Pain Assessments - VAS and PROMIS®

Pain Assessments (VAS and PROMIS®) will be completed by the subject at the screening visit and all six (6) follow-up visits after the Daily Pain Diary review. Pain assessments may also be done on the operative day (but prior to nerve block or surgical intervention) if the nerve block is planned to occur at this time.

The Visual Analog Scale (VAS) is a pain scale designed in such a way that it allows a study subject to rate their pain with minimum constraints.³⁴ Subjects will rate their current pain level by creating a mark on a 10 centimeter (100 millimeter) line. The distance measured from 0 millimeter to the patient's mark corresponds to the amount of pain the subject is currently experiencing. The open line gives the subject the greatest freedom to choose their pain's exact intensity. VAS data are recorded as the number of millimeters from the left of the line with the range 0-100, with 0 millimeter representing no pain, and 100 millimeters representing the most pain.

PROMIS[®] is a set of person-centered measures that evaluate and monitor physical, mental, and social health in adults and children. Measures are applicable to the general population and to those with

chronic conditions. For this study, PROMIS® measures will be used to monitor a subject's physical health/pain.

Quality of Life Questionnaires (FHSQ) Quality of Life Questionnaires (FHSQ) will be completed by the subject at visits 1, 4, 5, 6, 7, and 8.

3.6.2.1 Foot Health Status Questionnaire (FHSQ)

The FHSQ was developed to help better measure responsiveness in overall foot health status in 4 areas (foot function, foot health, footwear and foot pain).³⁵ The FHSQ's 4 scale have shown to be better predictors of foot responsiveness than other index rating scores.³⁶ The FHSQ bank of 19 questions demonstrate a high degree of content, criteria, construct validity and retest reliability and have been used as an outcome measure in clinical trials for a range of foot disorders.³⁷

3.6.5 Concomitant Medication Log and Daily Pain Medication Diary (Quantity and Class)

Concomitant Medication logs and Daily Pain Medications Diaries (quantity and class of pain medication treatments) being prescribed/administered by the subject will be collected. A Daily Pain Medication Diary will be provided to each subject to take home and complete or subjects will be sent reminders to complete their daily pain diaries via ePRO for those subjects that enroll in ePRO. Daily Pain Medication diaries will be completed by the study subjects each day and will be reviewed at all six (6) follow-up visits. The subject will present the Daily Pain Medication Diary at each study visit for review by the site team, and a new diary will be dispensed to the subject at each visit. The collected medication diary will be filed in the subject chart for record of the study visit and for CRF completion/review. The site team will also capture any non-pain concomitant medications the subject is taking at each study visit.

3.6.8 Daily Pain Diary

A daily pain diary will be provided to each subject at the Screening visit (visit 1), and a new diary will be dispensed to the subject at Visits 2 through 7 to track incidence, frequency and severity of pain (using a 10-point scale) on a daily basis. Similar to the pain medication diaries, subjects will complete the daily pain diary either on paper or through the ePRO module of the EDC. The diary will be reviewed and collected at each study visit (by the site team with the subject) prior to completing the scheduled pain assessments (VAS/PROMIS®).

Measures to Minimize/Avoid Bias

The following control measures will be put in place to minimize and/or avoid bias within the study.

- All Investigators selected for participation must have completed a foot and/or microsurgical fellowship.
- Investigators will have prior experience performing neurectomy procedures in the foot or ankle, and will either have prior experience implanting the Axoguard® Nerve Cap or will receive inservice training to ensure correct and consistent technique.
- For those Investigators who have not implanted the product within the 12 months prior to the initiation of the study; a training in-service and/or bioskills lab will be performed to refamiliarize the Investigator with the handling, utilization and placement of each test product.
- Standardized evaluation tools will be provided to each study center.
- During the comparative phase, 1:1 randomization will occur at the time of surgery.
- Subjects will be blinded to the assigned treatment group until they complete the study.

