3.7.1 Blinding

While blinding the surgeon to treatment is not possible, blinding the subject is possible and all efforts should be taken to preserve this blind. Randomization will be used to assign the subject to a study group intra-operatively therefore ensuring the subject is blinded to their treatment assignment. Direct verbal or written communication regarding treatment identification beyond what is required at the institution for documentation/recording the details of the surgical procedure should be avoided. Safety assessments should be performed by a qualified medical professional.

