3.9.1 Visit 1: Pre-Operative Screening

Once informed consent has been obtained, the subject will be assigned a screening number and the following pre-operative assessments will be performed at the Pre-Operative Screening visit

- 1. Assess Inclusion/Exclusion criteria
- 2. Obtain relevant vital signs (height / weight)
- 3. Identify relevant medical history
- 4. Demographics
- 5. Assess for Neuroma
- 6. Pain Assessments (VAS, PROMIS®) prior to nerve block
- 7. Pain Assessment (VAS) post nerve block (if applicable)
- 8. Quality of Life Questionnaires (FHSQ
- 9. Concomitant Medication review and Daily Pain Medication Diary issuance (treatments including quantity and class of pain medications, dispense and review with subject)
- 10. Dispense Daily Pain Diary (review instructions with subject)
- 11. For subjects with multiple neuromas, additional Neuroma Information must be captured for each neuroma treated.

3.9.2 Visit 2: Operative Day, Day 0

The following will be collected during the Operative Day:

- 1. Verify Inclusion/Exclusion criteria
- 2. Obtain Vital signs
- 3. Document Operative Information: description of nerve injury presentation and location, and implantation information see sequence below¹⁹
- 4. Randomization (comparative study only)
- 5. Pain Assessments (VAS, PROMIS®) prior to nerve block, if not performed during screening
- 6. Pain Assessment (VAS) post nerve block, if not performed during screening
- 8. Concomitant Medication review and Daily Pain Medication Diary review (treatments including quantity, quality and class of pain medications, review with subject and re-educate if needed)
- 9. Daily Pain Dairy (review with subject prior to Pain Assessments, re-educate if needed)
- 10. Adverse Events review

The following sequence of steps will take place intraoperatively for the Nerve Cap group: 19

- 1. After debridement and mobilization of the nerve stump, determine the nerve diameter in millimeters (mm).
- 2. Select an Axoguard® Nerve Cap to fit the nerve stump, accounting for post-operative swelling and to allow easy insertion of the nerve stump into the device. If there is no Axoguard® Nerve Cap that matches the diameter of the nerve stump, select the device that is one size larger.
- 3. Hemostasis of the proximal nerve stump must be achieved prior to beginning the entubulation procedure. If a tourniquet is used, release the tourniquet and achieve hemostasis before entubulating.

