 $X_{optimal}$ = Score of the optimal foot health

 $S_{optimal}$ = Highest score of the new scale

Foot Function:

 $X_{worst} = 20$

 $X_{optimal} = 4$

 $S_{optimal} = 100$

Foot Health:

 $X_{\text{worst}} = 10$

 $X_{\text{optimal}} = 2$

 $S_{\text{optimal}} = 100$

Footwear:

 $X_{\text{worst}} = 3$

 $X_{\text{optimal}} = 15$

[figure not shown]
 $S_{\text{optimal}} = 100$

Foot Pain:

 $X_{\text{worst}} = 20$

 $X_{\text{optimal}} = 4$

 $S_{\text{optimal}} = 100$

Daily Pain Diary

A daily pain diary will be provided to each subject at the Screening visit (V1) and a new diary will be dispensed to the subject at Visits 2 through 7 to track incidence, frequency, and severity of pain (using a 10-point scale) daily. The diary will be reviewed and collected at each study visit (by the site team with the subject) prior to completing the scheduled pain assessments (VAS/PROMIS). The diary will also help track the use of subject pain medicine administration by reminding the subject to complete the Daily Pain Medication Diary for any pain medication/treatment taken by the subject at the time of the foot pain.

Daily Pain Medication Diary

A Daily Pain Medication Diary will be provided to each subject to take home and complete each day and will be reviewed at all visits. The subject will present the medication diary at each study visit for review by the site team and a new diary will be dispensed to the subject at each visit. The diary will be used to summarize pain medications by any use.

Opioid pain medications taken will be converted to morphine milligram equivalent (MME) where such conversions are available to summarize pain medications by quantity of use. For opioid and non-opioid pain medications, the Medication Quantification Scale⁴ (MQS) conversion will be used to convert medications to a comparable score. The MQS is a broader approach to quantifying medication consumption that captures non-opioid classes of medications without an equivalency to morphine. Unlike MME, two factors (detriment weight and dosage level) multiplied together scale the medication to a single score. Additionally, drugs will be categorized according to type of medication and the quantity taken will be summarized.

Recurrence of Symptomatic Neuroma

Subjects will be assessed for recurrence of symptomatic neuroma at the 3, 6, 9, and, 12 Month visits. The assessment intervals for each visit are as follows:

- Month 3 Visit: 6 Weeks after Operative Day 0 until Month 3 Visit

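### Site staff review the pain diary with the subject before the primary VAS is marked, no blinded reviewer is required, and the baseline VAS may or may not follow such a review

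*Protocol*

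**What the plan says.** **Order of assessments.** Protocol 3.6.8 has the diary "reviewed and collected at each study visit (by the site team with the subject) prior to completing the scheduled pain assessments". Protocol 3.6.1 places the VAS and PROMIS "at the screening visit and all six (6) follow-up visits after the Daily Pain Diary review". SAP section 6, under the diary definition, repeats the rule: "The diary will be reviewed and collected at each study visit (by the site team with the subject) prior to" the pain assessments.

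**What the VAS asks.** Protocol 3.6.1: "Subjects will rate their current pain level by creating a mark on a 10 centimeter (100 millimeter) line". Under Protocol 3.5.2 and SAP 9.1.1, change from baseline in this score is the primary efficacy endpoint, at 3 months in the pilot and at 12 months in the comparative phase.

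**Blinding.** Protocol 3.7.1: "While blinding the surgeon to treatment is not possible, blinding the subject is possible". The same section asks staff to avoid communication that would identify the treatment, and SAP 7.2 prohibits it. Neither document says whether the staff who review the diary are blinded.

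**Before surgery.** The screening list in Protocol 3.9.1 reads "Dispense Daily Pain Diary (review instructions with subject", so the diary is only handed out and explained at that visit. The operative-day list in 3.9.2 has "Daily Pain Dairy (review with subject prior to Pain Assessments, re-educate if needed" and also "Pain Assessments (VAS, PROMIS®) prior to nerve block, if not performed during screening". SAP section 6 allows baseline to be either Day 0 or the screening period, according to what suits the analysis.

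**The concern.** The surgeon cannot be blinded, so the main protection for the primary result is that a blinded subject marks the scale. The stated order puts a conversation about recent pain before that mark, led by staff who are not required to be blinded. The item asks only about current pain, so the subject does not need a review of past entries to answer it. If that conversation shifted scores differently in the two arms, the shift would go straight into the treatment difference.

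The second issue is comparability over time. If diary review itself shifts the mark, a baseline taken without review and a follow-up taken after review are not measured under the same conditions. Because the baseline visit is left open, this can also differ from one subject to the next.

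**Working it through.** No figure in the documents quantifies this point, so the first two steps compare texts. The last two are illustrations on stated assumptions.

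**1. Which VAS scores follow a diary review**

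| VAS | Review beforehand? | Source |
|---|---|---|
| Screening (Visit 1) | Not of entries: the diary is first dispensed here | Protocol 3.9.1; the wording of 3.6.1 reads as if a review takes place |
| Day 0 (Visit 2) | Yes | Protocol 3.9.2, diary item |
| Visits 3 to 8 | Yes, by the stated rule | Protocol 3.6.1 and 3.6.8, SAP section 6 |

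The visit lists in Protocol 3.9.3 to 3.9.6 print the pain assessments above the diary item (at Visit 8, item 3 and then item 7), but they do not declare a sequence. Only the Visit 2 list states one. Sections 3.6.1 and 3.6.8 therefore give the operative rule, and the lists sit awkwardly with it. The SAP schedule also notes that Visits 1 and 2 can fall on the same day, in which case a Day 0 review would have little or nothing to cover.

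**2. Who conducts the review.** Protocol 3.6.8 says the site team. Protocol 3.7.1 calls only the surgeon unblindable and only the subject blinded. The bias-control list that follows 3.6.8 likewise blinds only subjects. No visible text makes the reviewer blinded or independent of the surgeon.

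**3. A shift equal in both arms.** Let diary review move every follow-up VAS by c mm, and let the true mean changes be D (device) and C (control). With an unreviewed baseline:

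- randomized contrast: (D + c) − (C + c) = D − C, so c cancels;
- pilot change: D + c, so c passes through in full.

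For the pilot, n = 15. With an assumed SD of change of 20, 25 or 30 mm, the standard error SD/√15 is 5.2, 6.5 or 7.7 mm.

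**4. A shift that differs by arm.** Inputs from the documents: 86 subjects randomized 1:1, so 43 per arm (SAP section 4), and two-sided alpha 0.05 (Protocol section 5). Assumptions: SD 20 to 30 mm, no true difference, and a differential shift b favouring the device. By the normal approximation, SE = SD × √(2/43), and the chance of a significant result favouring the device is Φ(b/SE − 1.96).

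Example, SD 25 and b = 5: SE = 25 × √(2/43) = 5.39; 5/5.39 − 1.96 = −1.03; Φ(−1.03) = 15.1%.

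| SD (mm) | SE (mm) | b = 0 | b = 2 | b = 5 | b = 10 |
|---|---|---|---|---|---|
| 20 | 4.3 | 2.5% | 6.7% | 21.2% | 64.0% |
| 25 | 5.4 | 2.5% | 5.6% | 15.1% | 45.8% |
| 30 | 6.5 | 2.5% | 4.9% | 11.8% | 33.9% |

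For scale, 5 mm is 25% (5/20) to 36% (5/14) of the 14 to 20 mm clinically significant difference cited in Protocol 1.1. Both the SDs and the shifts are assumptions; the available text gives neither.

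**The case against.** The strongest reply is that a subject who does not know the allocation still makes the mark, and that going through that subject's own pain entries discloses nothing about treatment. Both documents also restrict talk that would identify it. This stands against a reading that a reader might be tempted to make, namely that the diary review weakens the blind. The documents do not support that. What remains is narrower: the restriction covers treatment identification, not expectation or coaching about pain scores from someone who may know the allocation.

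Some other stronger readings also fail:

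- **The site team is unblinded.** The documents say this only of the surgeon. For other staff, blinding is unspecified.
- **The review comes immediately before the VAS.** The text says only that it comes before.
- **Staff re-educate subjects before the primary score.** Re-education appears only in the visit lists, not in 3.6.1, 3.6.8 or SAP section 6, and it is absent from the Visit 8 list. The screening item suggests that it concerns filling in the diary.
- **Baseline is always taken without a review and follow-up always with one.** This holds for a screening baseline. A Day 0 baseline follows a review under 3.9.2.
- **The baseline mismatch biases the randomized comparison.** A common shift cancels, as shown above. Randomization also takes place during surgery, so whether a baseline VAS followed a review cannot depend on the allocation.

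The pilot is open label, so the argument about staff who know the allocation has no between-arm meaning there.

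**Conclusion.** The point holds in this form. The stated rule puts a site-team diary review before the primary VAS, and nothing requires the reviewer to be blinded. Staff who may know the allocation therefore have an avoidable opportunity to influence the score. It applies to all six follow-up assessments of VAS and PROMIS, including the Month 3 and Month 12 primary scores. The documents do not allow its size to be estimated. The illustration shows only that, at 43 per arm, a differential of a few millimetres would matter.

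Separately, the plan does not fix whether the baseline VAS is taken with or without a diary review. Conditions can differ between baseline and follow-up, which is relevant to the pilot and to within-arm changes, and also between subjects. This is a change the sponsor should make because it is cheap and protects the primary endpoint; there is no evidence that bias has occurred.

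**What to change.** 1. Amend Protocol 3.6.1 and 3.6.8, the Visit 2 diary item in 3.9.2 and SAP section 6 so that at every visit the subject completes VAS and PROMIS alone, before any diary or medication review and before contact with the operating surgeon. If the present order must stay, require a diary reviewer who is blinded to treatment.
2. Reconcile the visit lists in Protocol 3.9 with that rule. Those for Visits 3 to 8 already print the VAS first and need only a statement that the order is binding. Correct the wording in 3.6.1 that implies a diary review before the screening VAS.
3. In SAP section 6, name one assessment as the baseline VAS for all subjects, before any comparison between groups is seen.

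**Cost.** Protocol 12.1 treats any change as an amendment, with ethics approval awaited unless the change is administrative, so a memo to sites is not enough. No visit, procedure or staff is added, and the sample size is unaffected. If the switch comes mid-study, scores will have been collected under two orders. Record the switch date and report a sensitivity analysis of the primary endpoint by assessment order; this shows the difference in conditions but does not remove it.

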3.7.1 Blinding

While blinding the surgeon to treatment is not possible, blinding the subject is possible and all efforts should be taken to preserve this blind. Randomization will be used to assign the subject to a study group intra-operatively therefore ensuring the subject is blinded to their treatment assignment. Direct verbal or written communication regarding treatment identification beyond what is required at the institution for documentation/recording the details of the surgical procedure should be avoided. Safety assessments should be performed by a qualified medical professional.

3.8 Randomization (comparative phase only)

In the pilot phase, the initial 15 subjects in will be assigned to open label treatment with Axoguard® Nerve Cap. In the subsequent comparative phase, subjects will be centrally randomized using an Interactive Web Response System (IWRS), OpenClinica, to undergo either neurectomy or implantation of the Axoguard® Nerve Cap in a ratio of 1:1. Only subjects meeting all inclusion and exclusion criteria shall be randomized.

3.9 Study Procedures

After written informed consent is obtained, a pre-operative screening visit (visit 1) will be conducted to assess eligibility for the study. At the Operative Visit (visit 2), pre-operative preparation, debridement

and mobilization of the nerve stump will be per performed in accordance with the Investigator's/Institution's standards-of-care. After interoperative confirmation of eligibility is determined, randomization will occur. For patients randomized to receive Axoguard® Nerve Cap, the investigator will determine nerve diameter and select an appropriately sized Axoguard® Nerve Cap to fit the nerve stump, accounting for post-operative swelling and sufficient to allow easy insertion of the nerve stump into the device. Entubulation should be conducted in accordance with the product instructions for use (see IFU appendix C). Photographs of the surgical site, neuroma prior to resection and post-treatment (i.e. surgical implant or resected end) should be taken, if possible. Wound closure and immobilization will occur based on the institution's standard of care. Subjects will be followed for a total of 12 months post-operatively. Standardized assessments will occur at each visit. Study assessment time points are summarized below and in the Schedule of Assessments (see Appendix B).

